5. Assessment of concomitant medication: all new medications administered to the subject will be recorded.

This visit will ALWAYS be performed at the study center by the investigative staff.

Day 2 Visit (48 hours Post-infusion)

The following assessments and/or procedures will be carried out at Day 2 (48 hours after the infusion \pm 60 minutes):

1. Laboratory testing:
 - Fibrinogen levels (not applicable for pediatric subjects weighing <30 kg): Plasma samples will be obtained for measurement of fibrinogen levels by two methods: fibrinogen activity (Clauss method) and fibrinogen antigen (ELISA). Samples taken 48 hours after the infusion will be analyzed for measuring fibrinogen levels for PK calculations by the central laboratory of the study.
 - Rotational thromboelastometry (not applicable for pediatric subjects): ROTEM will be performed on frozen plasma samples by the central laboratory and following parameters measured: CT, CFT, MCF, and α . Samples taken 48 hours after the infusion will be analyzed by the central laboratory of the study.
 - Standard coagulation tests (not applicable for pediatric subjects): following standard coagulation tests: TT, PT, and aPTT will be performed on frozen plasma samples at the central laboratory of the study.
 - Markers of activation of coagulation (not applicable for pediatric subjects): following tests, indicative of activation of the coagulation: D-dimer, ATIII, TAT, and F_{1+2} will be performed on frozen plasma samples at the central laboratory of the study.
2. Assessment of AEs: any new AE occurred will be recorded.
 - Subjects will be monitored for signs and symptoms of allergic/hypersensitivity reactions.
 - Subjects will also be monitored for signs and symptoms of arterial and venous thromboses.
3. Assessment of concomitant medication: all new medications administered to the subject will be recorded.

This visit, and all subsequent follow-up visits except Week 4 Visit may be conducted in the subject's home by designated study staff (eg, homecare nurses) if approved by the study subject and the investigator.

Day 4 Visit (96 Hours Post-Infusion)

The following assessments and/or procedures will be carried out at Day 4 (96 hours after the infusion \pm 60 minutes):

1. Laboratory testing:

- Fibrinogen levels: plasma samples will be obtained for measurement of fibrinogen levels by two methods: fibrinogen activity (Clauss method) and fibrinogen antigen (ELISA)

Samples taken 96 hours after the infusion will be analyzed for measuring fibrinogen levels for PK calculations by the central laboratory of the study.

- Rotational thromboelastometry (not applicable for pediatric subjects): ROTEM will be performed on frozen plasma samples by the central laboratory and following parameters measured: CT, CFT, MCF, and α .

Samples taken 96 hours after the infusion will be analyzed by the central laboratory of the study.

- Standard coagulation tests (not applicable for pediatric subjects): following standard coagulation tests: TT, PT, and aPTT will be performed on frozen plasma samples at the central laboratory of the study.

- Markers of activation of coagulation (not applicable for pediatric subjects): following tests, indicative of activation of the coagulation: D-dimer, ATIII, TAT, and F_{1+2} will be performed on frozen plasma samples at the central laboratory of the study.

2. Assessment of AEs: any new AE occurred will be recorded.

- Subjects will be monitored for signs and symptoms of allergic/hypersensitivity reactions.
- Subjects will also be monitored for signs and symptoms of arterial and venous thromboses.

3. Assessment of concomitant medication: all new medications administered to the subject will be recorded.

Day 6 Visit (144 Hours Post-Infusion)

The following assessments and/or procedures will be carried out at Day 6 (144 hours after the infusion \pm 60 minutes):

1. Laboratory testing:

- Serum clinical chemistry: laboratory test will include creatinine, BUN, TB, ALP, ALT, AST, LDH, glucose, sodium, potassium, chloride, and calcium.

Samples taken 144 hours after the infusion will be analyzed by the central laboratory of the study.

- Hematology: laboratory test will include CBC: RBC count, Hgb, Hct, MCH, MCHC, MCV, WBC count and differential, and platelet count.

Samples taken 144 hours after the infusion will be analyzed by the central laboratory of the study.

- Fibrinogen levels: plasma samples will be obtained for measurement of fibrinogen levels by two methods: fibrinogen activity (Clauss method) and fibrinogen antigen (ELISA).

Samples taken 144 hours after the infusion will be analyzed for measuring fibrinogen levels for PK calculations by the central laboratory of the study.

- Rotational thromboelastometry (not applicable for pediatric subjects): ROTEM will be performed on frozen plasma samples by the central laboratory and following parameters measured: CT, CFT, MCF, and α .

Samples taken 144 hours after the infusion will be analyzed by the central laboratory of the study.

- Standard coagulation tests (not applicable for pediatric subjects): following standard coagulation tests: TT, PT, and aPTT will be performed on frozen plasma samples at the central laboratory of the study.
- Markers of activation of coagulation (not applicable for pediatric subjects): following tests, indicative of activation of the coagulation: D-dimer, ATIII, TAT, and F_{1+2} will be performed on frozen plasma samples at the central laboratory of the study.

2. Vital signs: subject vital signs (T, RR, HR, SBP, and DBP) will be monitored
3. Assessment of AEs: any new AE occurred will be recorded.
 - Subjects will be monitored for signs and symptoms of allergic/hypersensitivity reactions.
 - Subjects will also be monitored for signs and symptoms of arterial and venous thromboses.
4. Assessment of concomitant medication: all new medications administered to the subject will be recorded.

Day 9 Visit (216 Hours Post-Infusion)

The following assessments and/or procedures will be carried out at Day 9 (216 hours after the infusion \pm 60 minutes):

1. Laboratory testing:
 - Fibrinogen levels: plasma samples will be obtained for measurement of fibrinogen levels by two methods: fibrinogen activity (Clauss method) and fibrinogen antigen (ELISA).

Samples taken 216 hours after the infusion will be analyzed for measuring fibrinogen levels for PK calculations by the central laboratory of the study.

- Rotational thromboelastometry (not applicable for pediatric subjects): ROTEM will be performed on frozen plasma samples by the central laboratory and following parameters measured: CT, CFT, MCF, and α .
- Samples taken 216 hours after the infusion will be analyzed by the central laboratory of the study.
- Standard coagulation tests (not applicable for pediatric subjects): following standard coagulation tests: TT, PT, and aPTT will be performed on frozen plasma samples at the central laboratory of the study.
 - Markers of activation of coagulation (not applicable for pediatric subjects): following tests, indicative of activation of the coagulation: D-dimer, ATIII, TAT, and F₁₊₂ will be performed on frozen plasma samples at the central laboratory of the study.
 - Viral panel (not applicable for pediatric subjects): viral monitoring for each adult subject will be performed at the central laboratory of the study according to the following table ([Table 4-7](#)), which provides a schedule of the virology testing on Day 9 (216 hours after the infusion).

Table 4-7 Virology Schedule for Day 9

Virus	Serology	NAT
Parvovirus B19 ¹	X (IgM & IgG)	X

¹ The samples drawn on Day 9 will be analyzed only in the event of negative results of NAT, IgM, and IgG analysis for the presence of B19 performed on Baseline sample.

- Retention sample (not applicable for pediatric subjects): an additional blood amount of approximately 5 mL will be drawn on Day 9 (216 hours after the infusion) in order to obtain a serum/plasma retention sample from each adult subject. The retention sample will be frozen and stored at the central laboratory of the study in the event that additional testing is required in the future for purposes of this study only.
2. Assessment of AEs: any new AE occurred will be recorded.
 - Subjects will be monitored for signs and symptoms of allergic/hypersensitivity reactions.
 - Subjects will also be monitored for signs and symptoms of arterial and venous thromboses.
 3. Assessment of concomitant medication: all new medications administered to the subject will be recorded.

Day 14 Visit (336 Hours Post-Infusion)

The following assessments and/or procedures will be carried out at Day 14 (336 hours after the infusion \pm 60 minutes):

1. Laboratory testing:

- Serum clinical chemistry: laboratory test will include creatinine, BUN, TB, ALP, ALT, AST, LDH, glucose, sodium, potassium, chloride, and calcium.

Samples taken 336 hours after the infusion will be analyzed by the central laboratory of the study.

- Hematology: laboratory test will include CBC: RBC count, Hgb, Hct, MCH, MCHC, MCV, WBC count and differential, and platelet count.

Samples taken 336 hours after the infusion will be analyzed by the central laboratory of the study.

- Fibrinogen levels (not applicable for pediatric subjects weighing <30 kg): plasma samples will be obtained for measurement of fibrinogen levels by two methods: fibrinogen activity (Clauss method) and fibrinogen antigen (ELISA).

Samples taken 336 hours after the infusion will be analyzed for measuring fibrinogen levels for PK calculations by the central laboratory of the study.

- Immunogenicity testing (not applicable for pediatric subjects): Serum/plasma samples to be tested for antibodies to fibrinogen
- Viral panel (not applicable for pediatric subjects): viral monitoring for each adult subject will be performed at the central laboratory of the study according to the following table ([Table 4-8](#)), which provides a schedule of the virology testing on Day 14 (336 hours after the infusion).

Table 4-8 Virology Schedule for Day 14

Virus	Serology	NAT
HAV ¹		X
HBV ¹		X
Parvovirus B19 ¹	X (IgM & IgG)	X

¹The samples drawn on Day 14 will be analyzed for a particular virus only in the event of negative results of analysis of NAT, IgM, and IgG for that particular virus performed on the samples from all previous visits.

- Retention sample (not applicable for pediatric subjects): An additional blood amount of approximately 20 mL will be drawn on Day 14 (336 hours after the infusion) in order to obtain a serum/plasma retention sample from each adult subject. The retention sample will be frozen and stored at the central laboratory of the study in the event that additional testing is required in the future for purposes of this study only.

2. Vital signs: Subject vital signs (T, RR, HR, SBP, DBP) will be monitored.
3. Assessment of AEs: Any new AE occurred will be recorded.
 - Subjects will be monitored for signs and symptoms of allergic/hypersensitivity reactions.
 - Subjects will also be monitored for signs and symptoms of arterial and venous thromboses.

4. Assessment of concomitant medication: all new medications administered to the subject will be recorded.

Day 21 ± 1 Day Visit

The following assessments and/or procedures will be carried out at Day 21 ± 1 days after the infusion:

1. Laboratory testing:

- Viral panel (not applicable for pediatric subjects): viral monitoring for each adult subject will be performed at the central laboratory of the study according to the following table ([Table 4-9](#)), which provides a schedule of the virology testing on Day 21 ± 1 day after the infusion.

Table 4-9 Virology Schedule for Day 21 ± 1 Day Visit

Virus	Serology	NAT
HAV ¹	X (IgM & IgG)	X
HBV ¹		X

¹The samples drawn on Day 21 will be analyzed for a particular virus only in the event of negative results of analysis of NAT, IgM, and IgG for that particular virus performed on the samples from all previous visits.

- Retention sample (not applicable for pediatric subjects): an additional blood amount of approximately 10 mL will be drawn on Day 21 ± 1 day after the infusion in order to obtain a serum/plasma retention sample from each adult subject. The retention sample will be frozen and stored at the central laboratory of the study in the event that additional testing is required in the future for purposes of this study only.

2. Assessment of AEs: any new AE occurred will be recorded.

- Subjects will be monitored for signs and symptoms of allergic/hypersensitivity reactions.
- Subjects will also be monitored for signs and symptoms of arterial and venous thromboses.

3. Assessment of concomitant medication: all new medications administered to the subject will be recorded.

Week 4 ± 3 Days Visit

The following assessments and/or procedures will be carried out at Week 4 ± 3 days after the infusion:

1. Physical assessment: physical examination by body systems performed by the investigator or its designee (eg, a medical doctor designated as sub-investigator).
2. Laboratory testing:
 - Immunogenicity testing (not applicable for pediatric subjects): serum/plasma samples to be tested for antibodies to fibrinogen.

- Viral panel (not applicable for pediatric subjects): viral monitoring for each adult subject will be performed at the central laboratory of the study according to the following table ([Table 4-10](#)), which provides a schedule of the virology testing on Week 4 ± 3 days after the Infusion Visit.

Table 4-10 Virology Schedule for Week 4 ± 3 Days

Virus	Serology	NAT
HAV ¹	X (IgM & IgG)	X
HBV ¹	X ²	X
HCV ¹		X
HIV-1 ¹		X

¹ The samples drawn on Week 4 ± 3 Days will be analyzed for a particular virus only in the event of negative results of analysis of NAT, IgM, and IgG for that particular virus performed on the samples from all previous visits.

² HBsAg

- Retention sample (not applicable for pediatric subjects): an additional blood amount of approximately 10 mL will be drawn on Week 4 ± 3 days after the Infusion Visit in order to obtain a serum/plasma retention sample from each adult subject. The retention sample will be frozen and stored at the central laboratory of the study in the event that additional testing is required in the future for purposes of this study only.

3. Assessment of AEs: Any new AE occurred will be recorded.

- Subjects will be monitored for signs and symptoms of allergic/hypersensitivity reactions.
- Subjects will also be monitored for signs and symptoms of arterial and venous thromboses.

4. Assessment of concomitant medication: all new medications administered to the subject will be recorded.

This visit will always be performed at the study center by the investigator.

Month 3 ± 7 Days Visit

This visit is not applicable to pediatric subjects. The following assessments and/or procedures will be carried out at Month 3 ± 7 days after the infusion:

1. Laboratory testing:

- Viral panel: viral monitoring for each subject will be performed at the central laboratory of the study according to the following table ([Table 4-11](#)), which provides a schedule of the virology testing on Month 3 ± 7 days after the Infusion Visit.

Table 4-11 Virology Schedule for Month 3 ± 7 Days

Virus	Serology	NAT
HBV ¹	X ²	
HCV ¹	X ³	X
HIV-1 ¹ and HIV-2 ¹	X ⁴	X ⁵

¹ The samples drawn on Month 3 ± 7 Days will be analyzed for a particular virus only in the event of negative results of analysis of NAT, IgM, and IgG for that particular virus performed on the sample from Day 0 Visit (Baseline).

² HBsAg

³ In case of HCV positive antibody screen, a recombinant immunoblot assay will be performed.

⁴ In case of HIV positive antibody screen, a Western blot assay for HIV-1 will be performed.

⁵ NAT for HIV-1 only.

- Retention sample: an additional blood amount of approximately 10 mL will be drawn on Month 3 ± 7 days after the Infusion Visit in order to obtain a serum/plasma retention sample from each subject. The retention sample will be frozen and stored at the central laboratory of the study in the event that additional testing is required in the future for purposes of this study only.
2. Assessment of concomitant medication: a registry of medications, other than the investigational product, administered to the subject.

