4.6.1.6 Fibrinogen Levels

Plasma samples will be obtained for measurement of fibrinogen levels by two methods:

1. Fibrinogen activity (Clauss method)
2. Fibrinogen antigen

Samples for fibrinogen determination will be taken at:

1. Screening Visit (up to 21 days prior to Infusion Visit): Sites that cannot perform fibrinogen levels determinations (by both Clauss and antigen method) locally will have a blood sample taken at Screening Visit and have it analyzed for this parameter by both methods at the central laboratory of the study for verification of the eligibility against the Inclusion/Exclusion criteria. In these cases, sample for the Inclusion/Exclusion criteria assessment will not be taken at Baseline Visit. Sample for PK will still be taken at Baseline Visit.

In order to allow sufficient time for samples shipment and analysis and reporting of results back to the site, the sample for determination of the eligibility should be drawn at least 14 days prior to the planned infusion.

2. Infusion Visit (Day 0):
 - i. For sites that have the capability of performing fibrinogen level determinations by both Clauss and antigen methods locally, a sample will be drawn within 24 hours of the scheduled infusion and analyzed at the local laboratory of the site in order to have the results available prior to the scheduled infusion in order to verify that the subject fulfills the inclusion criteria. In case fibrinogen levels determination for verification of the Inclusion/Exclusion criteria is performed at the screening visit, this sample will not be taken at Baseline Visit. Sample for PK as described below will still be taken at Baseline Visit.
 - ii. Immediately prior (within 60 minutes prior) to the scheduled infusion a sample will be taken and analyzed at the central laboratory for fibrinogen levels. The value to be used for PK calculations as baseline value will be the central laboratory one, unless there is any technical issue with the PK central laboratory measurement that recommends not using this value, in which case the value for the Inclusion/Exclusion criteria assessment could be used for this purpose.
 - iii. At 30 minutes (not applicable for pediatric subjects weighing <30 kg), 1 hour, 2 hours (not applicable for pediatric subjects weighing <30 kg), 4 hours (not applicable for pediatric subjects weighing <30 kg), and 8 hours after infusion end. These samples will be analyzed by central laboratory.

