3. Day 1 (24 hours post-infusion): central laboratory testing only

4. Day 2 (48 hours post-infusion): central laboratory testing only (not applicable for pediatric subjects weighing <30 kg)
5. Day 4 (96 hours post-infusion): central laboratory testing only
6. Day 6 (144 hours post-infusion): central laboratory testing only
7. Day 9 (216 hours post-infusion): central laboratory testing only
8. Day 14 (336 hours post-infusion): central laboratory testing only (not applicable for pediatric subjects weighing <30 kg)

The exact time and date of taking the samples for the PK analysis will be recorded by the study staff for the PK analysis.

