4.6.1.16 Retention sample

An additional appropriate volume of blood (specific volumes per visit indicated in [Section 4.6.2](#)) will be drawn in order to obtain a serum/plasma retention sample from each adult subject, with the exception of Day 0 pre-infusion sample, which will also be obtained from pediatric subjects. The retention sample will be frozen and stored in the event that additional testing is required in the future for purposes of this study only (ie, repeat testing, confirmation of virology results, or immunogenicity testing).

Retention samples will be drawn at:

1. Infusion Visit (Day 0): immediately prior (within 60 minutes prior) to the scheduled infusion. This sample will be also drawn from pediatric subjects. Additional samples will be drawn for enrolled adult subjects at 1 hour and 4 hours after completion of the infusion.
2. Day 9 (216 hours post-infusion, not applicable for pediatric subjects)
3. Day 14 (336 hours post-infusion, not applicable for pediatric subjects)
4. Day 21 ± 1 day post-infusion (not applicable for pediatric subjects)
5. Week 4 ± 3 days post-infusion (not applicable for pediatric subjects)
6. Month 3 ± 7 days post-infusion (not applicable for pediatric subjects)

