Samples must be taken within 60 minutes prior to the scheduled infusion to be analyzed by the central laboratory of the study.

- Immunogenicity testing (not applicable for pediatric subjects): serum/plasma samples must be taken prior to the scheduled infusion to be tested for antibodies to fibrinogen at the sponsor's laboratory.
- Viral panel (not applicable for pediatric subjects): viral monitoring for each subject will be performed at the central laboratory of the study by means of serology and NAT tests for the following viruses: HAV, HBV, HCV, HIV-1 and HIV-2, and B19. The following table ([Table 4-6](#)) provides a schedule of the virology testing on Day 0 (Baseline).

Table 4-6 Baseline Virology Schedule for Day 0

Virus	Serology	NAT
Hepatitis A virus (HAV)	X ¹ (IgM & IgG)	X ¹
Hepatitis B virus (HBV)	X ^{1,2}	X ¹
Hepatitis C virus (HCV)	X ¹	X ¹
Human immunodeficiency virus type 1 and type 2 (HIV-1 & HIV-2)	X ¹	X ^{1,3}
Parvovirus B19	X ¹ (IgM & IgG)	X ¹

¹ Sample will be always analyzed.

² Total anti-HBc (IgM & IgG).

³ NAT for HIV-1 only.

Samples must be taken within 60 minutes prior to the scheduled infusion to be analyzed by the central laboratory of the study.

- Retention sample: An additional blood amount of approximately 20 mL will be drawn within 60 minutes prior to the scheduled infusion in order to obtain a serum/plasma retention sample from each subject. The retention sample will be frozen and stored at the central laboratory of the study in the event that additional testing is required in the future for purposes of this study only.
- 3. Vital signs: subject vital signs (T, RR, HR, SBP, DBP) will be monitored within 60 minutes before the beginning of the infusion (baseline vital signs).
- 4. Height and weight: Subject height and weight will be measured for all subjects at Baseline Visit. Weight value will be used for calculation of dose to be administered.
- 5. Assessment of AEs: AE occurring at any time between signature of *Clinical Trial Informed Consent* and the Week 4 Visit will be reported.
 - Subjects will be monitored for signs and symptoms of allergic/hypersensitivity reactions occurring between the Baseline Visit and Week 4 Visit.
 - Subjects will be also monitored for signs and symptoms of arterial and venous thromboses occurring between the Baseline Visit and Week 4 Visit.

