8.2.4 LABORATORY PANELS

Laboratory tests will include:

1. Serum clinical chemistry: including creatinine, BUN, ALT, AST, ALP, LDH, TB, glucose, sodium, potassium, chloride and calcium.

2. Hematological parameters: CBC, including platelet count and differential leukocyte count.
3. Markers of activation of coagulation: different measures indicative of activation in the coagulation pathway (D-dimer, ATIII, TAT, F₁₊₂).

Blood specimens for laboratory tests will be collected at different time points throughout the study. Laboratory tests results will be collected in the corresponding CRF/eCRF entry. Abnormal (out of range) results will be flagged by the reporting laboratory. The investigator will be required to indicate the clinical relevance of out of range (abnormal) results. Laboratory results out of the normal range judged by the investigator as clinically relevant will be considered AEs.

In the case of markers of activation of coagulation, their relationship with plasma fibrinogen levels pre- and post-infusion will be studied.

In case of pediatric sampling, pediatric tubes would be provided to reduce the amount of blood drawn for lab works, including the complete elimination of virology, immunogenicity, and markers of activation of coagulation lab works. Pediatric subjects will not undergo Month 3 virology and immunogenicity follow-up visits, and their participation in the study will finish at the Week 4 Visit. Pediatric subjects weighing less than 30 kg will also have an even more reduced blood sampling schedule as detailed in [Table 4-4](#) and [Table 4-5](#):

- Day 0 - baseline (including the retention sample)
- Day 0 - 1 hour post-infusion
- Day 0 - 8 hours post-infusion
- Day 1 - 24 hours post-infusion
- Day 4 - 96 hours post-infusion
- Day 6 - 144 hours post-infusion and
- Day 9 - 216 hours post-infusion

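### The Day 0 retention draw is a flat volume of about 20 mL for every subject, and no smaller volume is written for children, including those under 30 kg

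*Protocol*

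**What the plan says.** Three protocol sections have to be read together.

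- **Section 4.6.1.16 (Retention sample)** asks for "An additional appropriate volume of blood (specific volumes per visit indicated in" Section 4.6.2. It limits retention samples to adults, "with the exception of Day 0 pre-infusion sample, which will also be obtained from pediatric subjects".
- **Section 4.6.2 (Infusion Visit, Day 0 - Baseline)** supplies the figure: "An additional blood amount of approximately 20 mL will be drawn within 60 minutes prior to the scheduled infusion". The bullet addresses every subject. The immunogenicity and viral-panel bullets just before it are marked as not applying to children, as are the retention draws at 1 hour, 4 hours, Day 9, Day 14, Day 21 and Week 4. This one carries no such mark.
- **Section 8.2.4 (Laboratory panels)** states the intention to spare children blood: "pediatric tubes would be provided to reduce the amount of blood drawn for lab works". It adds that children under 30 kg "will also have an even more reduced blood sampling schedule", and the first entry in that schedule is "Day 0 - baseline (including the retention sample". It gives no volumes.

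The reduction below 30 kg works by leaving out fibrinogen time points. Section 4.6.1.6 has, for instance, "Day 14 (336 hours post-infusion): central laboratory testing only (not applicable for pediatric subjects weighing <30 kg". Tables 4-4 and 4-5 attach the under-30 kg footnote only to fibrinogen samples; the retention sample is marked for children without it.

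**The concern.** The plan sets out to take less blood from children, and less again below 30 kg, yet the one retention sample it keeps for them has a single written volume that does not depend on body size. A site following the text would take the same 20 mL from a toddler as from an adult, within the hour before infusion, in patients whose condition Section 2.7 describes as a moderate to severe bleeding disorder.

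Small children are not ruled out. Section 5.1 sets an upper age limit but no lower limit of age or weight, and SAP Section 9.3 allows for an under-2 age group if the data permit. The sample is a contingency archive rather than an input to a planned analysis, so its volume can be scaled without touching any endpoint. What is at stake is avoidable blood loss in the smallest participants and a clear instruction to sites. No estimate or test in the SAP is affected.

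**Working it through.** **Inputs from the documents.** Retention volume: about 20 mL (Protocol 4.6.2). Applies to children: yes (4.6.1.16). Applies below 30 kg: yes (8.2.4; Tables 4-4 and 4-5). Smaller pediatric figure: none in the protocol or SAP. The 20 mL is a stated procedural volume, so there is no derivation behind it to reproduce.

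**Assumptions not in the documents.** Illustrative body weights of 10, 20, 30 and 70 kg, because expected pediatric weights are not given. Circulating blood volume of 70-90 mL/kg.

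**Formulas.**
- Draw per kg = 20 mL / weight.
- Share of blood volume = 20 mL / (weight x assumed mL/kg).
- Scaled draw = the smaller of 20 mL and rate x weight.

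| Weight | 20 mL per kg | Share at 90 mL/kg | Share at 70 mL/kg | Draw at 0.5 mL/kg | Draw at 20/70 = 0.29 mL/kg |
|---|---|---|---|---|---|
| 10 kg | 20/10 = 2.0 | 20/900 = 2.2% | 20/700 = 2.9% | 5 mL | 2.9 mL |
| 20 kg | 20/20 = 1.0 | 20/1800 = 1.1% | 20/1400 = 1.4% | 10 mL | 5.7 mL |
| 30 kg | 20/30 = 0.67 | 20/2700 = 0.7% | 20/2100 = 1.0% | 15 mL | 8.6 mL |
| 70 kg | 20/70 = 0.29 | 20/6300 = 0.3% | 20/4900 = 0.4% | 20 mL (cap) | 20 mL |

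Per kg, a 10 kg child gives 70/10 = 7 times what a 70 kg adult gives for this sample. At 0.5 mL/kg the 20 mL cap is reached at 20/0.5 = 40 kg, so heavier subjects would be unaffected. A 10 kg child would then give 5/900 to 5/700, or about 0.6-0.7% of blood volume.

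**What cannot be computed.** The volumes of the other baseline samples (chemistry, hematology, fibrinogen, ROTEM, coagulation) are not stated, so neither the total baseline draw nor the retention sample's share of it can be worked out.

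**The case against.** The strongest reply is that the protocol already deals with this in substance. The pediatric-tube statement in Section 8.2.4 stands in the paragraph that leads into the under-30 kg list, and that list names the retention sample. The natural reading is that the tube provision covers it. Section 4.6.1.16 also speaks of an appropriate volume, and 4.6.2 gives its figure only as approximate. Children are spared a great deal: adults give 20+20+20+5+20+10+10+10 = 115 mL over eight retention draws, children 20 mL in one, about 83% less. Children also skip the activation markers, immunogenicity and viral panel. Keeping one pre-infusion archive is deliberate, and because children have no baseline virology or antibody test, it may have to serve several assays later.

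Much of this stands. The intention is right, the sample should be kept, and a much smaller volume might not suffice. But intention and tubes do not give a site a number. The section named as the source of the volume gives only 20 mL, and the word approximately does not license a quarter of it.

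Two further inferences are tempting and should not be drawn:

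- A reader might infer that 20 mL of archive blood displaces the fibrinogen samples omitted below 30 kg. The documents give no volume for those samples. They are separate post-infusion time points, some on other days, and a smaller baseline archive would not restore them.
- A reader might take the 5 mL adult retention draw at Day 9 as proof that 5 mL is enough. That visit tests adults for parvovirus B19 only, and adults have seven other retention samples.

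**Conclusion.** The point holds as a gap between the protocol's stated aim and its only written instruction. Children, including those under 30 kg, are assigned the adult retention volume of about 20 mL at Day 0, equal to 2.0, 1.0 and 0.67 mL/kg at 10, 20 and 30 kg against 0.29 mL/kg at 70 kg. The 2.2-2.9% of blood volume at 10 kg depends on the assumed 70-90 mL/kg and on a child that small being enrolled, which the criteria allow but do not predict.

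A reader might infer that the draw is unsafe or exceeds a pediatric limit. The documents do not support that: they state no limit, the total baseline blood cannot be sized, and no harm is shown. The case for change is that a discretionary volume can be scaled to body size cheaply and in line with the plan's own aim. The change is worth making for any child still to be enrolled, and it does not bear on the validity of any analysis.

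**What to change.** In Section 4.6.2, Day 0 baseline, keep about 20 mL for adults and give children a smaller, weight-scaled volume: a fixed mL/kg with 20 mL as the maximum. A rate of 0.29 mL/kg would match a 70 kg adult; about 0.5 mL/kg would give 5 mL at 10 kg and 10 mL at 20 kg. These rates are illustrations. The sponsor's medical team should choose the figure after confirming that the resulting serum or plasma suffices for look-back virology and antibody testing, including repeats. Sections 4.6.1.16 and 8.2.4 should then cross-refer to it. Exclusion criterion 18 requires a pre-infusion storage sample but sets no minimum volume, so eligibility need not change.

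The cost is a sentence in 4.6.2, two cross-references and matching sample-handling instructions for sites. The real downside is less archived pre-infusion material from children, who have no other retention sample. That is why the volume should be reduced only as far as later testing allows, and the sample should not be removed.
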